3. ABSTRACT/SYNOPSIS

TITLE:	LONG-TERM NON-INTERVENTIONAL SAFETY STUDY OF EMICIZUMAB TREATMENT IN PATIENTS WITH MODERATE HAEMOPHILIA A AND SEVERE BLEEDING PHENOTYPE (STUDY BO44691, PASS)	
PROTOCOL NUMBER:	BO44691	
VERSION NUMBER:	2.0	
DATE OF SYNOPSIS:	November 2023	
EU PAS REGISTER NUMBER:	To be determined	
STUDIED MEDICINAL PRODUCT:	Emicizumab (RO5534262, ACE910, HEMLIBRA®)	
SCIENTIFIC RESPONSIBLE:		
MAIN AUTHOR:		
PHASE:	IV, non-interventional study	
INDICATION:	Moderate congenital Haemophilia A ($1\% \le FVIII \le 5\%$), without FVIII inhibitors and with severe bleeding phenotype	
MARKETING AUTHORISATION HOLDER:	Roche Registration GmbH [name]	

Rationale and Background

Haemophilia A (HA) is a congenital form of haemophilia causing a lack of coagulation factor VIII (FVIII). Bleeding often occurs in joints and can result in severely damaged and deformed joints; it can also occur in any other part of the body and can be life-threatening.

The goal of haemophilia treatment is to reduce the risk of bleeding and other complications of the disorder. Haemophilia treatment of more severe cases have traditionally relied on FVIII infusions that often poses a significant burden on the patient and even during prophylactic treatment patients can experience a high rate of bleeding events.

Hemlibra—F. Hoffmann-La Roche Ltd Protocol BO44691, Version 2.0

Emicizumab (Hemlibra®) is a recombinant, humanised, bispecific monoclonal antibody that mimics the function of activated FVIII without being structurally similar, meaning that emicizumab is not linked to the development or is affected by the presence of FVIII inhibitors. The use of subcutaneous (SC) injection as the route of administration also results in significantly lower patient burden of treatment.

In the European Union (EU), the marketing authorisation holder (MAH) submitted an extension of indication for Hemlibra to include routine prophylaxis of bleeding episodes in patients with congenital HA without FVIII inhibitors who have moderate disease ($1\% \leq$ FVIII \leq 5%) with severe bleeding phenotype.

On 15 December 2022, the committee for medicinal products for human use (CHMP) issued a positive opinion for this new extension of indication; European commission (EC) decision was received on 23 January 2023.

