8.3.1. Primary and Secondary Safety Variables

The primary safety variable is TE events as recorded in the data source.

The secondary safety variables are:

- TMA
- Serious systemic hypersensitivity reactions, including anaphylaxis
- SAEs (for definition of SAEs see section 10.1.2.)

The relationship to the treatment will be detailed according to available information in each registry. If this is not available in the registry, time to the first primary or secondary safety events will be described, for further details see section 8.7.

The reporting of AEs in the considered registers for further engagement differs, an overview is given in Table 3 and the details are provided below.

Table 3.	Reporting	of adverse	events among	the considered	data sources.
			U		

Data source	Country	Coding standard
UKNHD	UK	Local adaptation of EUHASS
FranceCoag	France	EUHASS (ICD-10 used for further classification of malignant disorders)
HemoNED	Netherlands	EUHASS
ATHNdataset	US	SNOMED, MedDRA
WBDR	Multi-country	Standardised module
CBDR	Canada	CHESS

UKNHD, UK National haemophilia database; **UK**, United Kingdom; **EUHASS**, European Haemophilia Safety Surveillance; **ATHNdataset**, American Thrombosis and Hemostasis Network; **US**; United States; SNOMED **CT**, Systemized Nomenclature of Medicine – Clinical Terms; **MedDRA**, Medical Dictionary For Regulatory Activities; **WBDR**, World Bleeding Disorders Registry; **CBDR**, Canadian Bleeding Disorders Registry; **CHESS**, Canadian Hemophilia Surveillance System; **ICD**, International Classification Of Diseases.

The European Haemophila Safety Surveillance (EUHASS) system is a pharmacovigilance program that aims to monitor the safety of treatments for patients with haemophilia and other inherited bleeding disorders in Europe through a prospective AE reporting system. The program started in October 2008 and includes participating centres located across more than 30 European countries. The following events are reported to EUHASS either as they occur or as a minimum at the end of every 3-month surveillance period (European Haemophilia Safety Surveillance, n.d.):

- Acute or allergic events
- Transfusion-transmitted infections
- Inhibitors
- Thromboses
- Malignancies
- New cardiovascular events
- Neurological events
- Unexpected Poor Efficacy
- Other AE Possibly Related to Concentrate
- Deaths

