For each event reported, data are collected on the patient's age, diagnosis and severity; as well as details about the product and batch numbers involved; and finally details about the event outcome and presence of other risk factors (Makris et al., 2011). Event-specific data are submitted anonymously using the Soundex coding system to avoid

Hemlibra—F. Hoffmann-La Roche Ltd

Protocol BO44691, Version 2.0

duplicate reporting. EUHASS data are not collected according to the medical dictionary for regulatory activities (MedDRA) classifications; however, AEs have been previously aligned to MedDRA preferred terms.

For the UKNHD data source, event reporting has been harmonised with the EUHASS program, and any reported event from participating centres are anonymised and automatically forwarded to EUHASS by the National Haemophilia Database (NHD). Yet, whenever a new inhibitor is reported, the UK Haemophilia Centre Doctors' Organisation (UKHCDO) requests more detailed information, which is not passed onto EUHASS. The additional data requested by the UKHCDO when a new inhibitor is reported include (World Federation of Hemophilia, 2009):

- Coagulation disorder, severity, and genotype if known
- Any relatives with inhibitors
- First inhibitor detection date and the reason for the test
- Inhibitor value at first detection and maximum value
- Any change in the value of factor VIII- or factor IX-coagulant (FVIII:C or FIX:C)
- Any change in bleeding pattern
- Treatment protocol before inhibitor development
- Time in chronological and exposure days from first dose to inhibitor development

The Canadian Hemophilia Surveillance System (CHESS) uses the same methodology as the EUHASS program (Dolan et al., 2014).

For the WBDR data source, an AE module is available at both baseline (when the patient enrolled in the registry) and follow-up visits. When an AE is reported, the participant centre must complete the following fields:

- Start date of onset (i.e., the date the patient first experiences the AE)
- Events (Infection, allergic reaction including anaphylaxis, TE event, TMA, lack of efficacy, injection site reaction or other event)
- Date of resolution (i.e., the date by when the patient stops experiencing the AE)
- Interventions

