centres to collect uniform and standardised data on people with HA or B, or von Willebrand Disease. As of February 2022, 96 participating centres from 46 countries had access to the WBDR (World Bleeding Disorders Registry, 2020). As of June 2023, a total of 10071 HA patients were estimated in the database, including 2987 with moderate HA. Data collection occurs at the level of participating treatment centres and includes a minimal data set that provides basic information on demographics, diagnostics, inhibitor status, bleeding events, joint disease, treatment, hospitalisation and mortality; as well as an extended data set that provides expanded details on the variables covered in the minimal dataset (Barbara Konkle et al., 2020).

Canadian Bleeding Disorders Registry (CBDR)

The CBDR, launched in July 2015, is a clinical database that collects information on virtually all patients affected by bleeding disorders in Canada, using a standardised dataset, data quality control processes, and incentivising mechanisms for Canadian Hemophilia Treatment Centres. As of June 2023, a total of 2799 HA patients were in the database, which included 299 patients with moderate HA. CHESS is a haemophilia surveillance system that was introduced in 2015, capturing data related to treatment safety and efficacy, plasma clotting factor utilisation and HRQoL data; and is compatible with the other data collection resources operating in Canada (Canadian Health Registry/ Canadian Hemophilia Assessment and Resource Management information System). The CBDR database is owned by the Association of Hemophilia Clinic Directors of Canada, and McMaster University is the data custodian. Patient demographics, clinical data, treatment usage and outcome data are collected via two main mechanisms: patients can enter information about their treatment and the bleeding events into the myCBDR app; and clinicians and others involved in the care of the patient can add specific data as part of documenting clinical interactions with the patient (lorio et al., 2022).

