8.7.2. Planned Analyses

For the analysis of the primary objective and secondary objectives 1, 2, and 3 the overall crude and crude stratified IRs will be calculated. The person-time of each patient will be based on the follow-up and censoring criteria presented in section 8.2.4. and 8.2.5.

For the calculation of crude IRs, the denominator will be the pooled person-time of all the patients within the cohort. The patient time-at-risk will be calculated from index date until the date of an incident event or censoring, whichever occurs first. All first events occurring during follow-up period will be counted in the total number of events. Crude IRs will be presented per 100 PY with 95% CI.

For the primary objective, the numerator will be the number of first TE events of all patients within the cohort. For secondary objectives 1, 2, 3 the numerator will be the number of first occurrences of any SAE; TMA events or serious systemic hypersensitivity reactions, including anaphylaxis; respectively.

For the analysis of secondary objective 4, calculation of crude stratified IRs of 1st TE events will be done. The events will be counted for each category/stratum of relevant pre-defined risk factors (see section 8.3.2.4. for a listing of considered risk factors). More details on the risk factor based tabulations will be presented in SAP.

For analysis of secondary objective 5, characteristics of TE events, SAEs, TMA, and serious systemic hypersensitivity reactions, including anaphylaxis (e.g., diagnosis and symptoms), will be tabulated. In addition, time to 1st TE event; time to 1st TMA event; time to 1st serious systemic hypersensitivity reactions, including anaphylaxis; and time to any 1st SAE event will be described by Kaplan-Meier curves.

For analysis of secondary objective 6, calculation of crude IR and crude incidence proportion of TE, TMA events, SAEs and serious systemic hypersensitivity reactions, **Hemlibra—F. Hoffmann-La Roche Ltd** Protocol BO44691, Version 2.0

including anaphylaxis, will be calculated and tabulated for FVIII prophylaxis use (yes/no) prior to emicizumab treatment.

Patient demographic and clinical characteristics will also be tabulated in relation to the AEs (TE events, SAEs, TMA events and serious systemic hypersensitivity reactions, including anaphylaxis) and in total.

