10.1. DEFINITIONS

10.1.1. Adverse Events (AEs)

According to the International Conference of Harmonisation (ICH), an AE is any untoward medical occurrence in a patient or clinical investigation subject administered a pharmaceutical product, regardless of causal attribution. An AE can therefore be any of the following:

- Any unfavourable and unintended sign (including an abnormal laboratory finding), symptom, or disease temporally associated with the use of a medicinal product, whether or not considered related to the medicinal product;
- Any new disease or exacerbation of an existing disease (a worsening in the character, frequency, or severity of a known condition);
- Recurrence of an intermittent medical condition (e.g., headache) not present at baseline (at the index date in the present study);
- Any deterioration in a laboratory value or other clinical test (e.g., electrocardiogram [ECG], X-ray) that is associated with symptoms or leads to a change in study treatment or concomitant treatment or discontinuation from study medicine.

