10.1.2. Serious Adverse Events (SAEs)

An SAE is any AE that meets any of the following criteria:

- Is fatal (i.e., the AE actually causes or leads to death)
- Is life-threatening (NOTE: The term "life-threatening" refers to an event in which the patient was at immediate risk of death at the time of the event; it does not refer to an event that hypothetically might have caused death if it were more severe)
- Requires or prolongs inpatient hospitalisation
- Results in persistent or significant disability/incapacity (i.e., the AE results in substantial disruption of the patient's ability to conduct normal life functions)
- Is a congenital anomaly/birth defect in a neonate/infant born to a mother exposed to study medicine
- Is a significant medical event in the physician's judgement (e.g., may jeopardise the patient or may require medical/surgical intervention to prevent one of the outcomes listed above)

Hemlibra—F. Hoffmann-La Roche Ltd Protocol BO44691, Version 2.0

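### Objective 1 has a single first-SAE rate that counts serious haemophilic bleeds together with all other serious harm; a non-bleed line would be a cheap addition

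*Protocol*

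**What the plan says.** **The rate.** Protocol section 8.7.2 defines the objective 1 rate: "the numerator will be the number of first occurrences of any SAE". On the denominator it says: "The patient time-at-risk will be calculated from index date until the date of an incident event or censoring, whichever occurs first". The synopsis repeats the same numerator.

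**The definition.** Section 8.3.1 lists the safety variable as "SAEs (for definition of SAEs see section 10.1.2" and so takes its definition from section 10. Section 10.1.1 counts as an adverse event "Any new disease or exacerbation of an existing disease". Section 10.1.2 makes an adverse event serious if, among other criteria, it is life-threatening or "Requires or prolongs inpatient hospitalisation". No section exempts haemophilic bleeds or reports them apart from other SAEs.

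**The population.** Section 8.2.6.1 selects patients for a severe bleeding phenotype: recent factor VIII prophylaxis, any earlier spontaneous bleed, or an annualised bleeding rate of at least 2. The synopsis says of bleeding that "it can also occur in any other part of the body and can be life-threatening".

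**The sources.** In section 8.3.1 the adverse-event options of the World Bleeding Disorders Registry (WBDR) that could take a bleed are among "lack of efficacy, injection site reaction or other event". Section 8.4 says that the same registry's minimal data set covers "inhibitor status, bleeding events, joint disease, treatment, hospitalisation and mortality". The EUHASS event list in section 8.3.1 has no plain bleed category.

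**The concern.** Objective 1 is meant to describe serious harm in patients on emicizumab. Serious bleeds are the disease that the drug is given to prevent. A rate that counts both moves with bleed control as well as with other harm, and a reader of the pooled figure cannot tell which has moved it.

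The second risk is uneven capture. If one source files a hospitalised bleed as an adverse event and another holds it only as a bleed record, the pooled rate combines two definitions. Differences by region (section 8.7.3), or by prior factor VIII prophylaxis (objective 6), could then reflect filing practice or bleeding tendency rather than other serious harm.

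**Working it through.** The protocol states no SAE rate and no serious-bleed rate, so no figure of its own bears on this point. Its one precision figure, 88% for 200 patients in section 8.5.2, concerns thromboembolic events and is unaffected. The check is therefore a reading of the text, followed by an illustration with assumed rates.

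**1. Does a hospitalised bleed fall within objective 1?** Section 8.3.1 points to 10.1.2, which builds on 10.1.1. A bleed that worsens a known condition and leads to admission meets both definitions, and there is no carve-out. By the text, it counts.

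**2. Does another planned analysis separate bleeds?**
- Sensitivity analysis 2 (Table 10) counts all events, so it picks up later SAEs, but it does not split bleeds from the rest. It also changes the follow-up rule, so it is not the objective 1 rate with bleeds removed.
- Objective 5 tabulates SAE diagnoses without a rate or time at risk by type. Its Kaplan-Meier curve is again for any first SAE.
- Thromboembolic events, thrombotic microangiopathy and serious hypersensitivity have their own first-event rates, which an earlier bleed does not end. No other non-bleed SAE has one.

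**3. Is capture alike across sources?** Table 3 ties UKNHD, FranceCoag and HemoNED to EUHASS or a local adaptation, and section 8.3.1 says that the Canadian system uses the same method. The nearest EUHASS entries for a bleed are unexpected poor efficacy, neurological events and deaths. WBDR has its own module, quoted above. ATHN is coded in SNOMED and MedDRA. The protocol does not say how any of them files a hospitalised bleed.

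**4. Illustrative share of bleeds.** Assume constant, independent rates: s for non-bleed SAEs (3 to 10 per 100 person-years) and b for bleed SAEs (2 to 10). The first-SAE rate is b + s, and the bleed share is b/(b + s).
- Lowest: b = 2, s = 10 gives 2/12 = 17%.
- Middle: b = 5, s = 5 gives 5/10 = 50%.
- Highest: b = 10, s = 3 gives 10/13 = 77%.

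If b = 0 the share is nil. For capture, take s = 5 and b = 10. A source that files every serious bleed as an SAE shows 15 per 100 person-years, and one that files none shows 5. That is the all-or-none extreme.

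**5. Is the non-bleed part understated?** Take 200 patients, 4 years, s = 0.05 and b = 0.10 per year.
- Patients with a first SAE of any kind: 200 × (1 − exp(−0.15 × 4)) = 90.2. Of these, 90.2 × 5/15 = 30.1 are non-bleed.
- Patients with at least one non-bleed SAE: 200 × (1 − exp(−0.05 × 4)) = 36.3.
- So 36.3 − 30.1 = 6.2 patients, or 17% of those affected, have their non-bleed SAE only after a bleed SAE.
- Person-time to first SAE: 90.2/0.15 = about 601 person-years. The non-bleed component is 30.1/601 = 5.0 per 100 person-years, which is exactly s.

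The person-time removed offsets the events removed. Under these assumptions the rate carries the non-bleed component in full; it is simply not shown.

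**The case against.** A reader might infer that the rate understates non-bleed SAEs, since a bleed ends the clock. Step 5 shows otherwise under constant, independent rates, because numerator and denominator are cut together. The 17% is a share of affected patients, not a bias in the rate.

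A reader might also infer that SAEs after a bleed are dropped. They leave only the objective 1 first-event rate. Sensitivity analysis 2 counts them, objective 5 describes SAEs by diagnosis, and the named risks keep their own clocks.

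The strongest remaining objection is that this is detail for the statistical analysis plan. Sections 8.3 and 8.7.1 leave operational definitions and category definitions to it, section 10 leaves event mapping to it, and it is not at hand. Table 2 also lists bleeding among haemophilia characteristics, not safety variables, so registries may file few bleeds as SAEs. First occurrence of any SAE is moreover a conventional and coherent measure. Much of this stands: how often bleeds enter is unknown, and the analysis plan may settle the mapping. But the protocol itself fixes the numerator, the clock and the SAE definition, and under those the mixed rate is the only one promised.

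**Conclusion.** The point holds as a cheap improvement, not as an error. By the protocol's definitions, the single objective 1 rate combines serious haemophilic bleeds with all other serious harm, and no planned analysis gives the non-bleed rate. The degree may differ by registry.

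The size cannot be taken from the protocol. The range of 17 to 77% only restates the assumed rates (3 to 10 and 2 to 10 per 100 person-years, constant and independent). It would fall towards nil if serious bleeds on treatment are rare or are not filed as adverse events. The documents do not support the stronger readings, that non-bleed SAEs are understated or lost. Nor do they require the non-bleed rate to become the main figure. The primary objective and its sample size are untouched.

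**What to change.** In section 8.7.2, keep the rate of the first SAE of any kind and add a line for the first SAE other than a haemophilic bleed, with time at risk that runs to that event or to censoring. Add the same line to the objective 6 table and to sensitivity analysis 2, there as a count of all non-bleed SAEs under that analysis's own follow-up rule. Derive a bleed yes/no flag from the SAE diagnosis already listed in Table 2, and state for each source whether bleeds count as SAEs.

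Put the flag and the extra clock into the common data model specification before extraction. Table 7 shows no patient-level access for WBDR and the Canadian registry, which hold 2987 + 299 = 3286 of the 5307 moderate patients (62%). Section 8.6 has such providers aggregate the data themselves, so a first-event clock left out of the specification could not be rebuilt from what they deliver.

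The cost is one extra row per SAE table, a simple rule for classing bleeds, and one more derived item for data providers. A separate serious-bleed outcome built from bleed records matched to hospital stays would cost more and is not needed here.

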This study does not include any formal comparison and is purely descriptive. A common data model (CDM) will be used to create aggregated data, either by the data source or by IQVIA. This CDM will define the level of aggregation and minimum information required to enable the statistical analysis of the study objectives. The aggregated datasets will be pooled for the statistical analysis.

For the primary objective, crude IRs for 1st TE events during the follow-up period per 100 PY will be described. For the calculation of crude IRs, the denominator will be the pooled person-time of all the patients within the cohort and the numerator will be all first events occurring during the follow-up period. In addition of crude IRs, incidence proportions will also be calculated.

For the analysis of secondary objectives 1, 2, 3, 4 and 6, crude IRs per 100 PY will be calculated and for secondary objective 5, descriptive tabulations will be done for SAE and TE events.

For secondary objective 1, 2, 3 the numerators will be the number of first occurrences of any SAE, 1st TMA events and 1st serious systemic hypersensitivity reaction events during the follow-up period, respectively. The denominators for the crude IRs will be the pooled person-time. For secondary objective 4, the events will be counted for each category/stratum of relevant pre-defined risk factors of TE events, to yield crude IRs of TE per category/stratum. For analysis of secondary objective 5, characteristics of TE events, SAEs, TMA events, and serious systemic hypersensitivity reactions, including anaphylaxis (e.g., diagnosis and symptoms), will be tabulated. In addition, time to the 1st

TE events, SAE, TMA events, and serious systemic hypersensitivity reactions, including anaphylaxis events will be described by Kaplan-Meier curves. For analysis of secondary objective 6, calculation of crude IR and crude incidence proportion of TE events, SAEs, TMA events, and serious systemic hypersensitivity reactions, including anaphylaxis, will be calculated, and tabulated for FVIII prophylaxis use (yes/no) prior to emicizumab treatment.

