8.2.2. Cohort Entry Period

The cohort entry period, when the patients will be assessed in the data source for inclusion in the study, will last from MA of emicizumab for use among moderate patients without inhibitors in each participating country until approximately Q4 2026, to allow for a minimum of 4 year of follow-up until the end of the study period.

This will allow for patients using emicizumab to be included in locations where emicizumab has been approved earlier for use among HA patients with moderate severity, e.g., the US and Canada, before EMA protocol approval. In addition, protocol approval might have occurred after initiation of reimbursement discussion in several locations in Europe. Patients who initiated emicizumab before protocol approval will be considered for inclusion as long as re-consent is not required by the data sources, all other inclusion and exclusion criteria are fulfilled, and no major data enhancement is needed.

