8.2.4. Follow-up Period

The study will allow for a minimum of 4 years of follow-up after the index date. The follow-up period will be the time period from index date (first emicizumab initiation) until, **Hemlibra—F. Hoffmann-La Roche Ltd** Protocol BO44691, Version 2.0

the end of the study period (anticipated Q4 2030), a maximum of 5 years of follow-up, or censoring.

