8.2.5. Censoring

Patients will be followed until the end of study period or when meeting any of the following censoring criteria, the reason for censoring will be described, whichever occurs first:

- Death
- End of observation, e.g., due to loss to follow-up, emigration, or disenrollment from the registry
- Discontinuation of emicizumab treatment (as defined in the exposure section 8.3.2.2.)

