8.3.2.2. Exposure Definition

Exposure will be based on dates of prescriptions and dispenses, and details on the numbers of prescriptions and doses, as reported in the data source. The start of exposure (index date) is defined as the first prescription or injection of emicizumab, as noted in the data source. An overview of the variables available to define exposure during follow-up can be seen in Table 4. All registers cover the haemophilia related treatments: emicizumab, aPCC, Eptacog alfa (activated), and Factor VIII transfusions.

If the registry does not include information on exact stop dates of treatment exposure, as in the case of HemoNED, treatment will be considered ongoing for as long as new prescriptions, injections or dispenses are noted in the data source and are consistent with continuous treatment. To accommodate non-perfect adherence or other situations where the series of prescriptions are part of a continuous exposure period, an additional 90 days will be added to exposure period, at the last noted injection or at the end of prescribed supply, corresponding to 3 times the half-life of emicizumab when the patient will be considered no longer affected by the drug (Hallare and Gerriets, 2023). If the patient has not filled another prescription or received an injection at the end of the added 90 days, the exposure period will end. The definition of exposure might differ between data source and will be further defined in the SAP. Reason for treatment discontinuation will also be collected where available. Exposure of other treatments of interest, that were given prior to the index date, will be defined using a similar methodology that will be detailed in the SAP.

Hemlibra—F. Hoffmann-La Roche Ltd Protocol BO44691, Version 2.0

Register	Country	Start / stop dates	Dosage	Frequency	Reason for treatment*
UKNHD	UK	Captured	Captured	Captured	Captured
FranceCoag	France	Good	Good	Derived	Good
HemoNED	Netherlands	Moderate (start only)	Captured	Captured	Captured
ATHNdataset	US	Good	Good	Good	Good
WBDR	Multi- country	Good	Good	Good	Good
CBDR	Canada	Good	Good	Good	Good

Table 4. Treatment information in each data source.

*Prophylaxis, on demand or other.

UKNHD, UK National Haemophilia Database; **UK**, United Kingdom; **ATHNdataset**, American Thrombosis and Hemostasis Network; **US**; United States; **WBDR**, World Bleeding Disorders Registry; **CBDR**, Canadian Bleeding Disorders Registry.

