8.7.4. Sensitivity Analyses

The study will include 4 sensitivity analyses which will be performed on the study objectives. The sensitivity analyses are presented in Table 10 using the HARPER table template for sensitivity analyses (Wang et al., 2023).

Hemlibra—F. Hoffmann-La Roche Ltd Protocol BO44691, Version 2.0

Sensitivity analysis	What is being varied? How?	Why? (What do you expect to learn?)	Strengths of the sensitivity analysis compared to the primary analysis	Limitations of the sensitivity analysis compared to the primary analysis
1	Censoring not done at the end of treatment.	To determine the impact of possible information bias arising from informative censoring and the impact of long-term effects. The approach will be similar to an ITT analysis.	Long-term effects could be masked by censoring at end of treatment. Furthermore, treatment cessation could be linked to AEs.	The causal nature of the relationship between event and end of treatment will be difficult to evaluate if the event occurs long after the end of treatment.
2	All events, not just the first, will be counted for the rate and follow-up continues until end of study period	To determine the impact of all irrespective of 1 st or subsequent outcomes during follow-up.	Full evaluation of the rate of AEs' burden across the follow-up.	All events during study period will measure the all-event rate, wherein all events (incident or subsequent) will be treated as independent. Events will be counted in the numerator for crude event rates and denominator will be the length of follow-up period until end of study period.
3	The maximum length of follow- up will not be set to five-years.	Further determine the long- term safety of emicizumab in the patient population.	Longer follow-up.	Longer follow-up will be correlated with geographical region, due to differences in time of MA, with a likely overrepresentation of patients with a follow-up longer than 5 years outside the EU.

 Table 10. Sensitivity analyses – rationale, strengths and limitations.

Hemlibra—F. Hoffmann-La Roche Ltd Protocol BO44691, Version 2.0

Sensitivity analysis	What is being varied? How?	Why? (What do you expect to learn?)	Strengths of the sensitivity analysis compared to the primary analysis	Limitations of the sensitivity analysis compared to the primary analysis

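### The planned crude incidence proportions have no time horizon and understate 4- or 5-year risk whenever patients are censored early

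*Protocol*

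**What the plan says.** For objective 6, section 8.7.2 of the protocol specifies "calculation of crude IR and crude incidence proportion of TE, TMA events, SAEs and serious systemic hypersensitivity reactions", tabulated by FVIII prophylaxis before emicizumab (yes/no). The synopsis (section 3, Data Analysis) repeats this and also says, under the primary objective, "In addition of crude IRs, incidence proportions will also be calculated". Section 8.7.2 does not mention proportions for the primary objective. No time horizon is given in either place.

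Follow-up varies between patients. Section 8.2.4 ends it at "the end of the study period (anticipated Q4 2030), a maximum of 5 years of follow-up, or censoring". Section 8.2.5 censors at death, at discontinuation of emicizumab and at "End of observation, e.g., due to loss to follow-up, emigration, or disenrollment from the registry". Cohort entry closes around Q4 2026, "to allow for a minimum of 4 year of follow-up until the end of the study period" (section 8.2.2).

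Two other parts of section 8.7.2 matter here. The crude incidence rate per 100 PY, with time at risk stopping at the first event or censoring, is the measure for the primary objective and for secondary objectives 1 to 3. Kaplan-Meier curves of time to first TE event, TMA event, serious hypersensitivity reaction and SAE are planned under objective 5.

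**The concern.** A crude proportion counts a patient who leaves after six months without an event exactly like one observed event-free for five years. With staggered exits and no stated horizon, the result is not the risk over any defined period. Read as a 4- or 5-year risk, it is too low as soon as anyone is censored early. Two groups with the same event rate will also show different proportions if they are observed for different lengths of time.

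This bears on objective 6, where the proportion is one of two measures shown side by side by prior prophylaxis and where the objective speaks of the impact of that prophylaxis. It also bears on the primary objective as the synopsis describes it, because a percentage is easily set beside percentages from other sources with other follow-up.

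**Working it through.** **Inputs.** TE rate 0.15 per 100 PY, 200 patients and mean follow-up of 4 years, so 800 PY (section 8.5.2). Potential follow-up of 4 to 5 years at the final extraction (sections 8.2.2 and 8.2.4). The protocol gives no discontinuation or loss rate and no SAE rate. These are assumed: censoring of 0 to 20 per 100 PY, SAEs at 5 or 10 per 100 PY.

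**The protocol's own figure.** In 800 PY the largest event count whose upper 95% Clopper-Pearson limit stays at or below 1 per 100 PY is 2. With 0.0015 × 800 = 1.2 events expected, the probability of at most 2 is 0.880, which matches the stated 88%. The protocol states no expected proportion for this study, so there is none to reproduce.

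**Formulas.** With constant event rate l, independent censoring rate d and horizon T:
- risk over T = 1 − exp(−lT)
- expected crude proportion = l/(l+d) × [1 − exp(−(l+d)T)]

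Example for TE, d = 10 per 100 PY, T = 4: 0.0015/0.1015 × [1 − exp(−0.406)] = 0.493%, against a risk of 1 − exp(−0.006) = 0.598%.

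**Results at 4 years.** The row d = 0 equals the true risk.

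| d per 100 PY | TE at 0.15 | TE shortfall, relative | TE shortfall, points | SAE at 5 (assumed) | SAE at 10 (assumed) |
|---|---|---|---|---|---|
| 0 | 0.598% | 0% | 0.00 | 18.1% | 33.0% |
| 2 | 0.575% | 4% | 0.02 | 17.4% | 31.8% |
| 5 | 0.542% | 9% | 0.06 | 16.5% | 30.1% |
| 10 | 0.493% | 18% | 0.11 | 15.0% | 27.5% |
| 20 | 0.412% | 31% | 0.19 | 12.6% | 23.3% |

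The largest TE shortfall, 0.19 points, is about 0.4 patients in 200.

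**Against 5-year risk.** The 5-year TE risk is 0.747%. With potential follow-up spread evenly over 4 to 5 years, the crude proportion runs from 0.673% (d = 0) to 0.443% (d = 20), which is 10% to 41% too low.

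**Two groups with the same TE rate, 4 years.** The ratio of crude proportions is 1.00 if both are censored at 5 per 100 PY. It is 1.10 for 5 against 10, and 1.32 for 5 against 20.

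**Regions, final main analysis.** Full follow-up of 5 against 4 years gives at most 0.747/0.598 = 1.25. If European entry is uniform from early 2023 to Q4 2026 (assumed), about 75% of entrants can reach 5 years and the rest average 4.5. The mean is then 4.87 years, and the ratio to a region with 5.00 years throughout is about 1.03.

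**Regions, sensitivity analysis 3 (no 5-year cap).** With assumed follow-up of 4–12 against 4–8 years, the TE ratio is 1.33 without early censoring, and 1.26 and 1.20 with d = 5 and 10 per 100 PY.

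**Comparison with the trial programme.** Section 8.5.2 cites 3 of 798 (0.38%) at a mean exposure of 2.65 years. At an unchanged 0.15 per 100 PY, 2.65 years gives 1 − exp(−0.003975) = 0.40% and 4 complete years give 0.60%. That is a factor of 1.5 from observation time alone.

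**The case against.** The strongest reply is that little rests on the proportion. The incidence rate is the main measure and already accounts for time at risk, and Kaplan-Meier curves are planned for all four outcomes. Section 8.7.1 calls the study purely descriptive and rules out formal comparison by prior prophylaxis. Horizon and denominator could also be set in the SAP, which is not at hand. For TE, with 1.2 events expected, sampling error far exceeds a bias of 0.2 points. All of this stands and limits the weight of the point. It does not remove it: the protocol itself names a crude proportion, places it beside the rate for objective 6, and lists the curves only under objective 5.

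A reader might infer that the prior-prophylaxis groups are not comparable. The documents do not support that, because nothing in them says discontinuation or loss differs by prior prophylaxis, and with equal censoring the ratio is 1.00.

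A reader might also take the Table 10 remark "Longer follow-up will be correlated with geographical region, due to differences in time of MA" as evidence of regional imbalance in the main analysis. It is given as a limitation of sensitivity analysis 3, which drops the cap. In the final main analysis potential follow-up is 4 to 5 years. Imbalance is possible at the interim extractions (Q2 2025 and Q2 2027, section 5), when European patients treated since January 2023 would have at most about 2.3 years in Q2 2025 and entrants where approval came earlier may have more. However, the protocol does not say that proportions will be reported then.

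Finally, a fixed-time estimate does not cure informative discontinuation. Sensitivity analysis 1 is the protocol's answer to that.

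**Conclusion.** The point holds in a limited form. A crude proportion without a horizon, under censored follow-up of unequal length, is a poor estimate of risk and is biased low when patients leave early. For TE the 4-year error is about 4% to 31% relative for assumed censoring of 2 to 20 per 100 PY, and at most about 0.2 percentage points. With an assumed SAE rate of 5 per 100 PY it is 0.7 to 5.5 points (18.1% against 17.4% to 12.6%).

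These sizes rest on constant rates, independent censoring and assumed censoring and SAE rates; deaths were left out. Comparisons between groups are sound on this measure only where follow-up and discontinuation are equal. Regional differences matter mainly in sensitivity analysis 3 and possibly at the interim extractions. The incidence rates and the study-size calculation are unaffected.

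**What to change.** In section 8.7.2 and the synopsis, replace the crude incidence proportion with the cumulative incidence at fixed times, for example 1, 2 and 4 years, with 95% CI. Take it from the time-to-first-event analyses already planned, treating death as a competing event (Aalen-Johansen), and show follow-up time for each group in the same table. State in both places whether it applies to the primary objective, since at present only the synopsis says so. If the simple fraction is kept, for instance for continuity with the trial programme's 3 of 798, label it a count summary and do not use it to compare groups.

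The cost is a change of wording and a few table cells. Dates of event, death and censoring are already among the study variables. The small downside is that registries without patient-level access (WBDR and CBDR in Table 7) must supply events, deaths and numbers at risk at the chosen times. For TE by subgroup the estimates will be very imprecise, as the crude proportions would be.
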